5.8. Other Analyses

5.8.1. Pharmacokinetics

Pharmacokinetics (PK) samples for measuring serum guselkumab concentrations will be collected from all participants at the specified visits as shown in the Schedule of Activities. All PK evaluations will be performed on the PK analysis set for the main study, defined as participants who have received at least 1 administration of guselkumab and have at least one post-dose sample collection. The PK analyses for LTE period will include all participants who participate LTE period.

Descriptive statistics (N, mean, SD, median, range, coefficient of variation (%CV) and IQ range) will be used to summarize guselkumab serum concentrations at each sampling time point. PK data may be displayed graphically, such as median +/- IQ range PK concentrations over time. The following analyses will be performed as appropriate:

- Summary of serum guselkumab concentrations at each visit
- Summary of serum guselkumab concentrations at each visit by baseline body weight quartiles
- Summary of participants with serum guselkumab concentrations below the lowest level of quantification x minimum required dilution (LLOQxMRD) at each visit
- Plot of median +/- IQ range serum guselkumab concentrations over time

If sufficient data are available, then population PK analysis using serum guselkumab concentration-time data will be performed using nonlinear mixed-effects modeling to estimate total systemic clearance and volume of distribution. Details will be given in a population PK analysis plan and the results of the analysis will be presented in a separate report.

The relationship between serum guselkumab concentrations (quartiles) at Week 28 and the proportion of participants achieving GC-free remission at Week 28 and Week 52 will be performed. The relationship between serum guselkumab concentrations and key secondary endpoints (e.g. GC-free remission through Week 52, time to first flare, and cumulative GC dose through Week 28 and Week 52) may also be performed. In addition, summary of change from baseline in CRP concentration (mg/L), ESR at Week 28 by serum guselkumab concentration quartiles at Week 28 will be performed when appropriate.

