To evaluate long-term efficacy of guselkumab in adult participants with new-onset or relapsing GCA	
The proportion of participants achieving GC-free remission from Week 52 (LTE Week 0) through Week 104 by visit (LTE Week 52)
 
The time to first GCA disease flare from Week 52 (LTE week 0) through Week 104 (LTE Week 52).

To evaluate the continued safety of guselkumab in adult participants with new-onset or relapsing GCA.	
Number/proportion of participants with TEAEs or SAEs from Week 52 (LTE Week 0) through Week 112 (LTE Week 60)
 
Number/proportion of participants with clinically significant abnormalities in vital signs and laboratory safety tests from Week 52 (LTE Week 0) through Week 112 (LTE Week 60)

To evaluate the PK and immunogenicity of guselkumab, in adult participants with new-onset or relapsing GCA.	
Mean (SD) serum concentrations of guselkumab from Week 52 through Week 104 (LTE Week 52) in participants receiving active study intervention.
 
Number/proportion of participants with antibodies to guselkumab in participants receiving active study intervention

Objectives	Endpoints
To explore the changes in PD markers and arterial vessel wall inflammation following administration of guselkumab in adult participants with new-onset or relapsing GCA in the LTE period.	Assessment of IL-23 pathway related and disease related biomarkers in serum and whole blood at Week 104 (LTE Week 52) Large-Vessel Imaging (FDG-PET/CT) changes from baseline and Week 52 at Week 104 (LTE Week 52) or flare
To explore changes in participant reported Clinical Outcome Assessments, pain and fatigue, and physician reported outcomes following administration of guselkumab in adult participants with new-onset or relapsing GCA in the LTE period.	Change from baseline on electronic patient-reported outcome (ePRO): Patient's Global Assessment of Disease Activity (PGA), Pain Assessment, Functional Assessment of Chronic Illness Therapy (FACIT)-Fatigue and short form-36 (SF-36) at Week 76 (LTE Week 24), Week 104 (LTE Week 52) or Flare visit. Change from baseline on clinician reported outcome: Physician's Global Assessment of Disease Activity (PhGA) at Week 76 (LTE Week 24) Week 104 (LTE Week 52) or Flare visit.

Refer to Section 8 for evaluations related to endpoints.

Definitions of Efficacy Endpoints:

Remission of GCA: No signs or symptoms of GCA and adherence to the 26-week taper without GCA flare.

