If a participant is in GC-free remission at Week 48, the participant will be informed of the possibility to participate in the LTE period and continue to receive study intervention. Study intervention will continue to be blinded, meaning that a participant will continue to receive the treatment that had been allocated to that participant (placebo or guselkumab) in the main study. After the Week 52 evaluations, if the participant is eligible and has consented for the LTE, the participants will continue to receive SC study intervention every 4 weeks starting at Week 52 (LTE Week 0) under this protocol's study extension until participants reach Week 100 (LTE Week 48) or until a participant experiences a GCA flare, or the participants discontinues treatment due to unblinding after the Week 60 DBL for the Main study, or until the Sponsor makes a decision not to continue this study, whichever occurs first. Participants who continue treatment as part of the study extension will be intermittently evaluated per the protocol for efficacy, PK, and safety. The LTE period is followed by a 12-week safety follow-up period after the last dose (a final efficacy visit 4 weeks after the last dose and a safety follow-up visit 12 weeks after the last dose). Participants that experience a flare should have have a Flare visit with assessments performed according to the SoA preferably within 1 week of having the flare and an early termination visit approximately 12 weeks after the last dose. In case a participant is diagnosed as having a flare during a study visit or shortly before a planned study visit, the Flare visit and regular visit can be combined. Overlapping procedures and assessments need only be performed once. The FDG-PET/CT scan can be scheduled separately from other assessments.

After the Week 60 DBL, the study will be unblinded to treatment. Any participants in the LTE that are on placebo will be informed and administration of study intervention will be discontinued. The participants may still continue in the study until Week 112 or until the end of the safety follow-up period in case they experienced a GCA flare.

A diagram of the study design is provided in Section [1.2](#).

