9.4.6. Other Analyses

Pharmacokinetic Analyses

The PK evaluable population is defined as all the participants who received at least 1 complete dose of guselkumab and had at least 1 valid blood sample drawn for PK analysis after their first dose of guselkumab.

Serum guselkumab concentrations will be summarized over time for all participants who receive at least 1 dose of guselkumab. Descriptive statistics will be calculated at each sampling timepoint. All serum concentrations below the lowest quantifiable concentration or missing data will be labeled as such in the concentration database. Concentrations below the lowest quantifiable concentration will be treated as zero in the summary statistics. Pharmacokinetic data may also be displayed graphically.

If feasible, population PK analysis of serum concentration-time data may be performed using nonlinear mixed-effects modeling. Details will be provided in a separate technical report.

Immunogenicity Analyses

The incidence and titers of antibodies to guselkumab will be summarized for all participants who receive at least 1 dose of guselkumab and have appropriate samples for detection of antibodies to guselkumab (ie, participants with at least 1 sample obtained after their first dose of guselkumab).

A listing of participants who are positive for antibodies to guselkumab will be provided. The maximum titers of antibodies to guselkumab will be summarized for participants who are positive for antibodies to guselkumab.

The incidence of neutralizing antibodies (NAbs) to guselkumab will be summarized for participants who are positive for antibodies to guselkumab and have samples evaluable for NAbs to guselkumab.

Other immunogenicity analyses may be performed to further characterize the immune responses that are generated.

Biomarkers/Pharmacodynamic Analyses

The biomarker analyses will characterize the effects of guselkumab to identify PD markers and biomarkers relevant to treatment, and to determine if these markers can predict response to guselkumab. Changes in serum analytes, RNA levels in whole blood and in single cells from PBMC, and leukocyte subset counts and frequencies in PBMC over time will be summarized by intervention group, in separate technical reports. Associations between baseline levels and changes from baseline in select markers and clinical response on primary and major secondary endpoints in Sections 9.4.2 and 9.4.3 will be explored and summarized in separate technical reports.

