If a participant is in GC-free remission at Week 48, the participant will be informed of the possibility to participate in the LTE period and continue to receive study intervention. Study intervention will continue to be blinded, meaning that a participant will continue to receive the treatment that had been allocated to that participant (placebo or guselkumab) in the main study. After the Week 52 evaluations, if the participant is eligible and has consented for the LTE, the participants will continue to receive SC study intervention every 4 weeks starting at Week 52 (LTE Week 0) under this protocol's study extension until participants reach Week 100 (LTE Week 48) or until a participant experiences a GCA flare requiring GC rescue medication, or the participants discontinue study intervention due to unblinding after the Week 60 DBL for the Main study, or until the Sponsor makes a decision not to continue this study, whichever occurs first. Participants who continue treatment as part of the study extension will be intermittently evaluated per the protocol for efficacy, PK, and safety. The LTE treatment period is followed by a 12-week safety follow-up period after the last dose (a final efficacy visit 4 weeks after the last dose and a safety follow-up visit 12 weeks after the last dose). Participants that experience a flare should have a Flare visit with assessments performed according to the SoA of the protocol preferably within 1 week of having the flare and an early termination visit approximately 12 weeks after the last dose. In case a participant is diagnosed as having a flare during a study visit or shortly before a planned study visit, the Flare visit and regular visit can be combined. Overlapping procedures and

assessments need only be performed once. The FDG-PET/CT scan can be scheduled separately from other assessments.

After the Week 60 DBL, the study will be unblinded to treatment. Any participants in the LTE that are on placebo will be informed and administration of study intervention will be discontinued. The participants may still continue in the study until Week 112 or until the end of the safety follow-up period in case they experienced a GCA flare.

An overview of the long-term extension (LTE) period is presented in [Figure 2](#).

Figure 2: Schematic Overview of the Long-Term Extension (LTE) Period

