4. POPULATIONS (ANALYSIS SETS) FOR ANALYSIS

For purposes of analysis, the following populations are defined:

Analysis Sets	Description
Enrolled Analysis Set	All participants who signed the ICF
Randomized Analysis Set	The randomized analysis set includes all participants who were randomized in the study.
Full Analysis Set (FAS)	The full analysis set (FAS) includes all randomized participants who received at least 1 administration of study intervention.
Per Protocol (PP)	
The per protocol analysis set (PP) includes a subset of participants in the full analysis set (FAS) who were in general compliance with the protocol. General compliance is defined as having no major protocol deviations that could have an impact on the efficacy assessment per clinical judgement. This analysis will be used for the primary endpoint. Participants will be excluded from this analysis as below:
 
 • who did not meet the inclusion criteria 3, 4, 6, 8 in the protocol; • who met the exclusion criteria 1, 6, 22, 24 in the protocol;

Analysis Sets	Description
	
 • who discontinued study intervention for reasons other than lack of efficacy or an AE of worsening of GCA, or missed at least two scheduled study agent administrations prior to Week 28. 
Participants who did not complete all scheduled study intervention administration due to intercurrent events (discontinued the study intervention due to lack of efficacy or an AE of worsening of GCA, or participants who started prohibited medications or therapy during the study that could improve GCA, or received a rescue medication for a GCA flare) will be included in the per protocol analysis and the data handling rules for these intercurrent events specified in Section 5.3.2 and Section 5.3.3 will be applied.

Safety Analysis Set	The safety analysis set includes all participants who received at least 1 dose of study intervention.
Pharmacokinetics Analysis Set	All participants who received at least 1 administration of guselkumab and have at least one valid post-dose blood sample drawn for PK analysis.
Immunogenicity Analysis Set	All participants who received at least 1 administration of guselkumab and have at least one post-dose sample collection.
Pharmacodynamic Analysis Set	All participants who received at least 1 administration of study intervention and have at least one post-dose sample collection.

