5.8.1.1. Data Handling Guidelines

Unless otherwise specified, the following data handling guideline will apply to PK analyses:

- All serum concentration summaries for a particular timepoint will include data obtained from treated participants at the timepoint of interest without imputing any missing data
- A concentration not quantifiable (below LLOQ) will be treated as 0 in the summary statistics and shown as the lower limit of quantification (<LLOQ) in the data listings

- The data from a participant who meets one of the following dosing deviation criteria will be excluded from the by-visit data analyses and from that point onwards:
 - Discontinue guselkumab administrations
 - Skipped a guselkumab administration
 - Received incomplete/incorrect dose
 - Received incorrect study agent
 - Received additional dose

Of note, serum guselkumab concentrations prior to the first of such events will be included in the summaries. In addition, if a participant has an administration outside of dosing window, the concentration data collected at and after that will be excluded from the by-visit data analyses. Additional exclusions for PK data to be implemented based on TV-GDL-00362. All participants and samples excluded from analysis will be documented in the Clinical Study Report.

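### SAP 5.8.1 defines the LTE pharmacokinetic population as everyone in the extension, placebo participants included, contrary to the LTE endpoint, the PK analysis set and Protocol 9.4.6

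*SAP*

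**What the plan says.** SAP 5.8.1 first limits the main-study PK evaluations to participants who were given guselkumab and have a post-dose sample. It then sets a different population for the extension: "The PK analyses for LTE period will include all participants who participate LTE period".

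Four other places bear on who should be in that analysis:

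- **Endpoint.** Protocol Section 3, repeated in SAP 1.1, defines the LTE PK endpoint as "Mean (SD) serum concentrations of guselkumab from Week 52 through Week 104 (LTE Week 52) in participants receiving active study intervention".
- **Analysis set.** SAP Section 4 defines the PK set as "All participants who received at least 1 administration of guselkumab and have at least one valid post-dose blood sample drawn for PK analysis". It adds LTE versions of the full analysis and safety sets, but none for PK.
- **Protocol method.** Protocol 9.4.6 says "Serum guselkumab concentrations will be summarized over time for all participants who receive at least 1 dose of guselkumab", with no separate rule for the LTE.
- **Who is in the LTE.** SAP 1.2 (and Protocol 4.1) says: "a participant will continue to receive the treatment that had been allocated to that participant (placebo or guselkumab) in the main study". Placebo participants stop injections following the Week 60 database lock but may stay in the study to Week 112.

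On data handling, SAP 5.8.1.1 says "A concentration not quantifiable (below LLOQ) will be treated as 0 in the summary statistics" and that summaries for a timepoint "will include data obtained from treated participants at the timepoint of interest". The PK outputs listed in SAP 5.8.1 are the by-visit summary, the summary by weight quartile, the count below the quantification limit and the median plot. None mentions intervention groups.

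**The concern.** Within one paragraph the SAP gives the right population for the main study and a wider one for the LTE. This is a stated rule, not a missing detail, and it conflicts with the endpoint it serves. A programmer who follows it would put placebo participants into the guselkumab concentration tables with zeros. The LTE mean and median would fall, and some participants would count as below the quantification limit simply because they were on placebo. A programmer who drops them would be departing from the SAP.

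At stake is the description of long-term exposure under the SC regimen. The endpoint is exploratory and descriptive, and no primary or secondary comparison depends on it.

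**Working it through.** **1. Does any other rule remove placebo participants?** SAP 5.8.1 says PK samples are collected from all participants, so placebo samples will exist. The exclusions in SAP 5.8.1.1 are dosing deviations: stopping or skipping guselkumab, or receiving a wrong dose, wrong agent or extra dose. A placebo participant dosed as planned meets none of them. The restriction to treated participants does not say treated with what, and placebo participants do receive study intervention. Where the SAP wants an arm split in the LTE it says so (5.6.2 for efficacy, 5.7 for safety); 5.8.1 does not.

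**2. Inputs.** Planned sizes are 34 guselkumab and 17 placebo, with Week 28 remission rates of 80% and 40% (SAP Section 3). The documents give no LTE entry rate and no figure for LTE concentration. The only stated figure built on these inputs is the 82% power. It reproduces with a pooled-variance Z test, a continuity correction and two-sided alpha 0.10:

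- pooled rate = (6.8 + 27.2)/51 = 0.667
- null SE = √(0.667 × 0.333 × (1/17 + 1/34)) = 0.140
- alternative SE = √(0.24/17 + 0.16/34) = 0.137
- correction = 0.5 × (1/17 + 1/34) = 0.044
- power = Φ((0.40 − 0.044 − 1.645 × 0.140)/0.137) = 0.82

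This confirms the planning inputs as read. It says nothing about LTE entry.

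**3. Effect on the mean.** Assume every placebo sample is below the limit and so counts as 0, both arms are sampled equally, and the arms are pooled. Let M be the guselkumab-arm mean and s the placebo share of samples:

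pooled mean = (1 − s) × M + s × 0 = (1 − s) × M

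The understatement is therefore s, where pP and pG are the entry rates on placebo and guselkumab:

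s = 17·pP / (17·pP + 34·pG)

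| Entry rate, placebo / guselkumab (assumed) | Placebo entrants | Guselkumab entrants | s |
|---|---|---|---|
| 0% / 80% | 0 | 27.2 | 0% |
| 10% / 80% | 1.7 | 27.2 | 5.9% |
| 20% / 60% | 3.4 | 20.4 | 14.3% |
| 40% / 80% (Week 28 planning rates) | 6.8 | 27.2 | 20.0% |
| 40% / 60% | 6.8 | 20.4 | 25.0% |
| 40% / 50% | 6.8 | 17.0 | 28.6% |
| 50% / 50% | 8.5 | 17.0 | 33.3% |

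For placebo entry of 10-40% and guselkumab entry of 50-80%, s runs from 5.9% to 28.6%. It exceeds 33.3% only if placebo participants enter at a higher rate than guselkumab participants.

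**4. Other summaries.** The proportion below the quantification limit is at least s. The pooled median is the guselkumab arm's (0.5 − s)/(1 − s) quantile; at s = 0.20 that is 0.30/0.80, the 37.5th percentile. The SD also changes, but by an amount that depends on the between-participant variability, which the documents do not give. I leave it unquantified.

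**5. With the population restricted to guselkumab recipients,** s = 0 and the bias disappears.

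**The case against.** The strongest reply is that other text already limits the analysis. The endpoint in SAP 1.1, the PK set in SAP Section 4 and Protocol 9.4.6 all confine PK to guselkumab recipients. The 5.8.1.1 exclusions are framed around guselkumab dosing, and that section also points to an internal guideline on exclusions that is not available here. The LTE analysis follows unblinding, so an analyst would know which samples are placebo and would probably drop them or tabulate by arm. This stands in part: pooling placebo zeros is one reading of the plan, not a settled intention. It does not cure the sentence. SAP 5.8.1 is the only place that sets an LTE PK population, and it sets one that conflicts with all the others.

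A reader might infer that the LTE mean will be about 20% too low. The documents do not support that as a fact. It requires Week 28 planning rates to serve as LTE entry rates, equal sampling in both arms, and pooling. LTE entry in fact depends on Week 52 completion, no flare through Week 52, a completed taper without rescue, no related SAE or severe AE, and willingness to continue (Protocol 5.1, criterion 19). The share may also differ by visit, because placebo dosing stops after the Week 60 lock and participants then off treatment may not count as treated at that timepoint.

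A reader might also expect the unquantifiable values to be mistaken for lost exposure or anti-drug antibodies. That is speculation. The immunogenicity set is limited to guselkumab recipients, and allocation will be known.

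**Conclusion.** The point holds as a contradiction in the SAP: the LTE PK population in 5.8.1 is wrong against the endpoint, the PK analysis set and Protocol 9.4.6. Its numerical effect is conditional. With the arms pooled, unquantifiable values set to 0 and equal sampling, the LTE mean is understated by the placebo share. That share is 20% if entry follows the Week 28 planning rates and 6% to 29% over the assumed entry ranges, with 0% and 33% at no placebo entry and equal entry. If results are shown by arm or limited to guselkumab recipients, the bias is nil. The consequence is confined to a descriptive exploratory endpoint, but the sentence should be corrected before the LTE analysis.

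**What to change.** Replace the LTE sentence in SAP 5.8.1 with:

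> PK analyses for the LTE period will include participants in the PK analysis set who received at least 1 guselkumab administration at or after Week 52.

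This agrees with the endpoint and follows the pattern of the LTE sets already in SAP Section 4. It would also help to state in SAP 5.8.1.1 that treated participants means those treated with guselkumab. The cost is a sentence or two in the SAP, with no new data and no change to study conduct.

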5.8.1.1. Data Handling Guidelines

Unless otherwise specified, the following data handling guideline will apply to PK analyses:

- All serum concentration summaries for a particular timepoint will include data obtained from treated participants at the timepoint of interest without imputing any missing data
- A concentration not quantifiable (below LLOQ) will be treated as 0 in the summary statistics and shown as the lower limit of quantification (<LLOQ) in the data listings

- The data from a participant who meets one of the following dosing deviation criteria will be excluded from the by-visit data analyses and from that point onwards:
 - Discontinue guselkumab administrations
 - Skipped a guselkumab administration
 - Received incomplete/incorrect dose
 - Received incorrect study agent
 - Received additional dose

Of note, serum guselkumab concentrations prior to the first of such events will be included in the summaries. In addition, if a participant has an administration outside of dosing window, the concentration data collected at and after that will be excluded from the by-visit data analyses. Additional exclusions for PK data to be implemented based on TV-GDL-00362. All participants and samples excluded from analysis will be documented in the Clinical Study Report.

